7.8 Multiplicity Adjustment

The key secondary endpoints will be tested sequentially in the order of Reading Accessibility Index and then BCVA at the two-sided significance level 0.05. For example, if the hypothesis for the primary endpoint, Maximum Reading Speed, is rejected at 0.05 level, then Reading Accessibility Index will be tested at 0.05 level. Further, if the hypothesis for Reading Accessibility Index is rejected at 0.05 level, then BCVA will be tested at 0.05 level. If the hypothesis for the primary endpoint is not rejected at 0.05 level, then no hypothesis testing will be performed for the key secondary endpoints.

All other analyses are exploratory and will not be corrected for multiplicity.

7.9

7.10 Subgroup Analyses

Data may be summarized within subject subgroups of interest based on potentially relevant demographic, and clinical factors, such as age, nonsense mutation stop codon type (UGA, UAG, UAA), and/or baseline efficacy parameters, baseline VA, baseline iris area, and corneal keratopathy.

7.11 Post Hoc/Exploratory Analyses

Correlations between subject characteristics and outcome measures, and correlations among outcomes measures may be explored using regression models or other appropriate techniques.

8 CHANGES FROM PROTOCOL-SPECIFIED ANALYSES

Modifications to the planned statistical analyses should be minimized. Nonetheless, the data obtained from the study may indicate that the planned analyses are inappropriate or that additional analyses need to be performed. The study report will document any deviations from the planned analyses.

9 LIST OF PLANNED TABLES, FIGURES, AND LISTINGS

Tables are categorized and numbered in accordance with ICH E3 guidelines. Each table, figure and listing are presented by treatment arm. Efficacy tables will be provided both for ITT and Efficacy Evaluable populations. Accountability tables will also include an overall column. Listings will be sorted by treatment, subject identification, and by visit, if multiple visits exist.

10 MISSING DATA HANDLING

10.1 Handling Missing Efficacy Data

Missing data for the primary efficacy endpoint will be imputed through Week 48 using last observation carried forward (LOCF) as the primary method of imputation for the efficacy and ITT analysis populations.

As a sensitivity analysis to the use of LOCF, multiple imputation (using SAS PROC MI and SAS PROC MIANALYZE) will also be used to impute missing endpoint data. Missing data at week 48 will be imputed for the primary endpoint for the ITT population only. Missing data predictors will be baseline MRS, MNREAD baseline parameters of reading acuity index, critical print size, reading acuity, and subject age. Twenty iterations will be generated with a prespecified seed number of 20191015 using the Markov Chain Monte Carlo (MCMC) method.

A second sensitivity analysis will be performed using a tipping point approach. The best and worst MRS change will be selected over the entire sample. These values will be rounded to one decimal places. All ataluren-treated subjects with missing endpoint data will be imputed with the worst value and all placebo treated subjects with missing endpoint data will be imputed with the best value and a p-value derived. Next, all ataluren-treated missing values will be replaced by the next worst value all placebo-treated missing data will be replaced by the next best value and a p-value derived. This process will be continued until all ataluren-treated missing data are replaced with the best value and all placebo-treated missing data are replaced by the worst value. The point at which the p-value “tips” from non-significance to significance will be noted relative to its order and number of analyses performed. In the event that all permutations are statistically significant, then it can be concluded that imputation does not result in a false positive.

Efficacy data will not be imputed for the open-label study period.

If any needed/permitted surgical treatment is performed during the study, and as a consequence, any assessment outcomes are affected significantly due to the surgical procedure, these assessment outcomes on and after the surgery will be set as missing and the last assessment prior to the surgery will be used for later assessment time points.

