5 DEFINITIONS

Adverse Event

An adverse event (AE) is any untoward medical occurrence associated with the use of a drug (investigational medicinal product) in humans, whether or not it is considered related to the drug. An adverse event can therefore be any unfavorable and unintended sign (including an abnormal laboratory finding), symptom, or disease in a study subject who is administered study drug in this study. A specific list of occurrences that should be reported as AEs is provided in section 9.1.1 of the study protocol. Subjects must be followed for adverse events for at least 28 days after the last dose of ataluren administration, or until any drug-related adverse events and/or ongoing serious adverse events (SAEs) have resolved or become stable, whichever is later. Any event that starts within 35 days (to account for visit window) after last dose of ataluren will be summarized.

Adverse events will be graded for severity using Common Terminology Criteria for Adverse Events (CTCAE) Version 4 grading, where 1=Mild, 2=Moderate, 3=Severe, 4=Life-threatening, and 5=Fatal.

Relationship to study treatment will be coded using the following categories: Unrelated, Unlikely related, Possibly related, and Probably related. In summaries where relatedness is dichotomized to related or not, Unrelated and Unlikely related will be classified as not related and Possibly related and Probably related will be classified as related.

Serious Adverse Event:

A serious adverse event is defined as an adverse event that

- Results in death
- Is life-threatening (patient is at immediate risk of death from the event as it occurred)
- Requires in-patient hospitalization (formal admission to a hospital for medical reasons) or prolongation of existing hospitalization
- Results in persistent or significant disability/incapacity
- Results in a congenital anomaly/birth defect

Treatment-Emergent AE:

A TEAE is any AE that begins or increases in severity after the initial dose of study drug and within 5 weeks of the last dose of study drug.

Age

Subject's age is defined as from date of birth to randomization date. The formula used is (randomization date – date of birth+1) / 365.25.

Ataluren Exposure

The duration of exposure to ataluren treatment is defined as the last dose date minus the first dose date + 1 day.

Baseline

For any variable, unless otherwise defined, baseline is the last assessment taken prior to the first study drug administration.

Change from Baseline

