The arithmetic difference between a post-baseline value and the baseline value:

Change from Baseline = (Post-baseline Value – Baseline Value)

Percentage Change from Baseline = [(Post-baseline Value – Baseline Value) / Baseline Value] x 100

End of Double-masked study period

End of double-masked study period is at Week 48 (day 337 ± 28 days), unless terminated early.

End of Study

End of study is at Week 144 (day 1008 ± 7 days), unless terminated early.

Early termination from study

Early termination would be assigned to the visit whose visit window included the termination date. In the event that an early termination visit does not fall within a nominal visit window, then the termination visit will be assigned to the visit closest to that date. If duplicate data result from the assignment of a termination visit, then the values measured last will be selected for analysis.

Enrollment date

Enrollment date will be assigned after confirmation of eligibility has been received from PTC Therapeutics, but not after the first day of study drug administration.

Study drug

Study drug in this study is ataluren (PTC124) or placebo.

Randomization date

Randomization date is the day the subject is assigned a randomization number on study Day 1.

Study Day 1

Day 1 is defined as the first day that study drug is administered to the subject.

Study Day

Day on study = Starting from Day 1

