6.3 Efficacy Analysis Populations

The efficacy analysis population will include subjects for the ITT analysis population who have a baseline value and at least 1 post-baseline value. Subjects will be analyzed as treated. Analyses based on the efficacy analysis population will be supportive of those performed on the ITT population.

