7.7 Efficacy Analysis

All efficacy analyses will be conducted in both ITT population as the primary analysis. Visual acuity, corneal keratopathy, and iris area will also be analyzed using the efficacy analysis population as a supportive analysis.

The primary efficacy analysis will be by analysis of covariance (ANCOVA) where baseline Maximum Reading Speed (OU) and age will be included as covariates, with treatment as a fixed effect. LS means for the two treatment arms will be provided along with 95% confidence intervals.

To assess treatment effect on the change from baseline in secondary endpoints, general linear models/ANCOVA models, with baseline adjustment and treatment as factors will be used. For the analysis of MNREAD endpoints, age will be included as a continuous covariate; all other secondary endpoints will include age stratum as a factor in the model.

To adjust for other potential effects, some other appropriate statistical models, e.g., ANCOVA models, and/or mixed effect models, may be explored. The p-value of testing treatment difference will be provided. The trend of assessments overtime may be assessed. A summary of the efficacy endpoints listed above will also be provided by visit to assess the trend. Tests of trend, if performed, would include repeated measures over visits with an appropriate covariance structure fitted (first order autoregressive). The effect of linear time would be fit along with its product with treatment to test for differences in trend over time between the two treatment arms. If missing Week 48 assessments for the primary efficacy endpoint exist, sensitivity analyses will be conducted. The reasons of missing will be reported. Analysis results for data with and without imputations (using methods defined in Section 10.1) will be compared.

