Appendix A Schedule of Events

The types and timing of data to be recorded are summarized in Table 1 (Stage 1, double-masked period), Table 2 (Stage 2, open-label period), and Table 3 (open-label sub-study).

Table 1. Schedule of Events (Stage 1)

Protocol Activities		Screening				Double-Masked Treatment			
Day±Window	Week	-28	-4	1 ^a	1	169±28	24	337±28	48/ End of Stage 1 ^b
Visit		1		2		3			4
Informed consent		X							
Medical and ophthalmic history ^c		X							
Serum viral screen		X							
Physical exam		X		X					X
Height and weight		X		X		X			X
Vital signs		X		X		X			X
Ophthalmoscopy		X		X		X			X
Hematology, biochemistry, urinalysis		X				X			X
Serum β-HCG ^d		X		X		X			X
Study drug and diary dispensing				X		X			X
Study drug administration				X		X			X
Study drug compliance and return						X			X
Collect diary						X			X
Adverse events				X		X			X
Concomitant meds		X		X		X			X
MNREAD				X					X
████████████████████				X		X			X
Slit-lamp examination ^e				X		X			X
Slit-lamp photography				X		X			X
OCT				X		X			X
Fundus photography				X		X			X
Humphrey visual fields				X					X
BCVA (visual acuity and refraction) ^f		X		X		X			X
████████████████████				X		X			X
████████████████████				X		X			X
████████████████████ blood				X		X			X
sample for plasma PK ^g									If feasible (i.e., during surgery for glaucoma, cataracts, etc.)

Abbreviations: β -HCG, beta-human chorionic gonadotropin; BCVA, best corrected visual acuity; ETDRS, Early Treatment Diabetic Retinopathy Study; [REDACTED]; LEA, LEA Symbols Visual Acuity Test System; MNREAD, Minnesota Low Vision Reading (MNREAD) Acuity Charts; OCT, optical coherence tomography; PK, pharmacokinetic(s)

^a All study and laboratory assessments on the first day of treatment must be done prior to in-clinic administration of the first dose.

^b Open-label study drug administration will start at the end of Stage 1 (Visit 4/Week 48).

^c Should include capture of available historical values for ocular assessments included in this study, such as visual acuity, [REDACTED], etc.

^d Sample taken only for female subjects of childbearing potential.

^e Slit-lamp examination should precede [REDACTED] measurement.

^f Visual acuity and refraction will be assessed using the Early Treatment Diabetic Retinopathy Study (ETDRS) or an age-appropriate alternative (e.g., LEA).

Table 2. Schedule of Events (Stage 2)

Protocol Activities		Open-Label Treatment						End of Study)/ Early Termination ^a		Follow-Up ^b	

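### Stage 1 MNREAD is scheduled only at Day 1 and Week 48, so on the plain reading the primary LOCF scores baseline-only subjects as 0% change, and the multiple imputation meant to check it omits treatment arm

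*SAP*

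**What the plan says.** **Endpoint and populations.** SAP 3.1 defines the primary endpoint as percent change in binocular Maximum Reading Speed (MRS) from Day 1 to Week 48. Under SAP 10.1, missing values "will be imputed through Week 48 using last observation carried forward (LOCF) as the primary method of imputation", in both the efficacy and the ITT populations. SAP 6.2 makes ITT the primary efficacy population; it requires randomization and one dose, not a post-baseline value. SAP 6.3 restricts the supportive efficacy population to subjects "who have a baseline value and at least 1 post-baseline value".

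**Schedule.** SAP Appendix A states: "The types and timing of data to be recorded are summarized in Table 1 (Stage 1, double-masked period"). In that table the MNREAD row is marked at Visit 2 (Day 1) and Visit 4 (Week 48) only. The visit lists in Protocol 8.1.1.2 to 8.1.1.4 agree: MNREAD is named at Visits 2 and 4 and is absent from the readable part of the Visit 3 list, some lines of which are redacted.

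**Early discontinuation.** Protocol 8.2 and Protocol 10 ask discontinuing subjects to complete the end-of-study assessments, which include MNREAD. SAP 5 places that visit in the window that contains it. If no window does, "then the termination visit will be assigned to the visit closest to that date"; if duplicates result, "then the values measured last will be selected for analysis". SAP 5 also says that "baseline is the last assessment taken prior to the first study drug administration".

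**Checks on LOCF.** The multiple imputation in SAP 10.1 lists baseline MRS, three other baseline MNREAD parameters and age as predictors. Treatment arm is not listed, and imputation by arm is not stated. A tipping-point analysis is planned (SAP 10.1), as is a comparison of results with and without imputation (SAP 7.7). SAP 9 adds: "Efficacy tables will be provided both for ITT and Efficacy Evaluable populations".

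**Surgery.** Under SAP 10.1, if surgery has significantly affected an outcome, the values from the surgery onward are set to missing and the last pre-surgery value is used instead.

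**The concern.** LOCF is normally meant to carry an on-treatment value. Stage 1 schedules no MNREAD between baseline and Week 48, so unless a usable termination test exists, the only value to carry is the pre-treatment one. The subject then counts as unchanged by definition.

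This analysis yields the primary p-value, and SAP 7.8 lets the Reading Accessibility Index and then BCVA be tested only if the primary hypothesis is rejected. With the sample reduced to 24 (SAP 2.5), a few subjects can matter.

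Two further features add to it. An imputation model without arm fills both arms from one pooled prediction, which pulls them together. The surgery rule discards an observed value according to how that value turned out, with no threshold or assessor given. Protocol 6.2.1.1 keeps site staff masked, but that does not supply a criterion. For MRS in Stage 1 the replacement is normally baseline, so again 0%.

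**Working it through.** **Plan's own figures.** The documents give no missing rate and no SD for MRS, so there is no plan figure to reproduce on this point. The power statement in SAP 7.1 does not enter into it.

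**Step 1: the carried value.** By the percent-change formula in SAP 5, with baseline B carried forward: 100 × (B − B)/B = 0% for any B > 0.

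**Step 2: which termination values are usable.** Scheduled days are 1, 169 and 337. The midpoints are (1 + 169)/2 = Day 85 and (169 + 337)/2 = Day 253. A termination MNREAD after about Day 253 counts as Week 48. One between about Days 85 and 253 counts as Week 24 and is carried to Week 48. One before about Day 85 is closest to Visit 2, and the SAP does not say how it is then used.

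**Step 3: bias.** Let mA and mP be the baseline-only fractions on ataluren and placebo, g the placebo mean percent change and D the true difference, with missingness at random within arm.

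Expected LOCF estimate = (1 − mA)(g + D) − (1 − mP)g

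Bias = −mA(g + D) + mP·g

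If mA = mP = m, the bias is −mD whatever the value of g.

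**Step 4: numbers.** Assumed: 16:8 (24 subjects at 2:1, an upper bound because Protocol 8.3.15 does not require MNREAD under age 8) and SD 20 points. Rejection rates come from 20,000 simulated trials per scenario, using ANCOVA on treatment, baseline and age.

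| g, D | Baseline-only subjects | Expected LOCF estimate | Rejection, LOCF | Rejection, observed data only |
|---|---|---|---|---|
| +10, 20 | one per arm | 20 − 0.0625×30 + 0.125×10 = 19.4 | 52% | 50% |
| +10, 20 | 25% both | 20 − 7.5 + 2.5 = 15.0 | 30% | 42% |
| +10, 20 | 25% ataluren only | 20 − 7.5 = 12.5 | 19% | 49% |
| +10, 20 | 25% placebo only | 20 + 2.5 = 22.5 | 68% | 46% |
| −20, 10 | 25% both | 10 + 2.5 − 5 = 7.5 | 12% | 14% |
| −20, 10 | 25% ataluren only | 10 + 2.5 = 12.5 | 30% | 16% |
| −20, 0 | 25% ataluren only | 0 + 5 = +5.0 | 8.4% | 4.8% |

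The bias can also vanish or reverse:
- g = −20, D = 0, 25% in both arms: +5 − 5 = 0.
- g = −20, D = 10, mA = 25%, mP = 12.5%: +2.5 − 2.5 = 0.
- g = −20, D = 30, 25% on ataluren only: −0.25 × 10 = −2.5, against ataluren.

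**Step 5: imputation without arm.** Take g = +10, D = 20 and 25% missing in both arms. The pooled observed mean is (2/3)×30 + (1/3)×10 = 23.3. The arm means become 0.75×30 + 0.25×23.3 = 28.3 and 0.75×10 + 0.25×23.3 = 13.3, a difference of 15.0. Simulation with 20 imputations gave 14.4 and, in a separate run, 14.6, against 20.1 to 20.2 with arm included. Rejection was 6% to 15% without arm and 31% to 45% with it, depending on the predictors and the degrees-of-freedom method, which the SAP does not name.

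**Step 6: cross-check at the plan's effect size of 1.06 SD.** At 16:8, no placebo change and 25% missing in both arms, the mean estimates were 0.78 (LOCF), 0.75 (imputation without arm) and 1.04 (with arm).

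**The case against.** The strongest reply is that much of the remedy is already planned. SAP 10.1 prescribes LOCF for the primary endpoint in the efficacy population too, which excludes baseline-only subjects, and SAP 9 promises tables for it. Against that, SAP 7.7 says: "Visual acuity, corneal keratopathy, and iris area will also be analyzed using the efficacy analysis population as a supportive analysis". MRS is not named there, but at most this shows that SAP 7.7 and 10.1 disagree. The unimputed comparison is planned too, and the tipping-point analysis treats the arms separately. All of this is genuine mitigation. It is supportive only; the ITT result still decides the primary test.

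The scenarios are also severe. A baseline-only subject must miss a Week 48 visit with a ±28-day window and also lack a usable termination test that the protocol asks for. The decline scenario is weaker still: Protocol 2.1 describes decline in visual acuity and gives no rate, whereas Protocol 13.2.3.3 describes MRS as speed not limited by print size. Observed-data ANCOVA is unbiased here only because values were made missing at random within arm. These points stand and limit what can be said about size.

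A reader might infer more than the documents support:
- *That scoring 0% biases the estimate whenever reading speed changes, or that under decline ataluren-only missingness always favours ataluren.* The counter-examples in step 4 rule out both.
- *That a termination test in the first weeks would overwrite the Day 1 value.* The duplicate rule read alone suggests it, but the baseline definition already bars a post-dose value.
- *That the SAP expressly orders baseline to be carried.* It is silent. On the other reading these subjects have no primary value and the LOCF figures do not apply.

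**Conclusion.** The concern holds in limited form. On the plain reading, the primary ITT analysis assigns 0% change to baseline-only subjects. Equal missingness shrinks a true difference by the missing fraction; unequal missingness with a common trend can favour either arm. The documents support no single direction and no particular size. The effect is negligible with one subject per arm under improvement and substantial at 25%, assuming 16:8, SD 20 and missingness at random within arm.

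The omission of arm from the imputation model does not depend on how LOCF is read. With balanced missingness it produces nearly the same shrinkage as LOCF, so agreement between the two would be false reassurance.

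The surgery trigger is a secondary point: it is undefined and depends on the outcome, and no rate is available to size it. Together these justify correcting the SAP before unmasking. They do not show that the trial's result would be wrong.

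**What to change.** 1. Add treatment arm to the multiple imputation model, or impute by arm.
2. Do not carry the Day 1 value forward in the primary analysis. Use the ANCOVA on observed Week 48 values and on the termination values that the plan already maps to Week 24 or Week 48, and state the assumption: missing at random given arm, baseline and age. Keep zero change as a sensitivity analysis labelled *baseline carried forward*, and keep the tipping-point analysis.
3. State that a termination MNREAD before about Day 85 neither replaces baseline nor stands in for Week 48, and that the subject is treated as missing at Week 48.
4. Replace the surgery trigger with a data rule that does not depend on the observed outcome and is fixed before unmasking. Report results with the observed post-surgery values alongside. Which of the two is primary is an estimand choice for the sponsor.
5. Reconcile the surgery carry-forward to later time points with the statement in SAP 10.1 that open-label efficacy data are not imputed.

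**Cost.** SAP wording only. Baseline-only subjects leave the primary estimate and its standard error rises: at g = +10, D = 20, to 9.5 from 9.1 with one missing per arm and to 10.5 from 9.3 with 25% missing in both.

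Carrying mid-trial termination values leaves some bias. Suppose that in each arm 12.5% are baseline-only and 12.5% have a termination value at half the 48-week change. LOCF then gives (0.75×30 + 0.125×15) − (0.75×10 + 0.125×5) = 24.375 − 8.125 = 16.25. The proposed analysis gives 24.375/0.875 − 8.125/0.875 = 18.57, against a true 20.

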2.4 Study Design

This is a Phase 2, multicenter, stratified, randomized, double-masked, placebo-controlled study with a 4-week screening period, a 144-week treatment period, an optional 96-week open label sub-study, and a 4-week post-treatment follow-up period (either study completion or early termination). A minimum of 36 subjects with nonsense mutation aniridia who are ≥ 2 years of age are planned for enrollment into this study at investigator sites in US and Canada.

During the 4-week screening period, subjects will be assessed for eligibility.

Eligible subjects will enter the 144-week treatment period consisting of two stages:

- Stage 1 (Weeks 1 to 48) during which subjects will receive either ataluren or placebo in a masked fashion;
- Stage 2 (Weeks 49 to 144) during which subjects will receive open-label ataluren.

Eligible subjects will be randomized in a masked 2:1 fashion to either ataluren or placebo. Randomization will be stratified by age: ≤ 10 years versus > 10 years. Masked study drug will be dosed three times a day: 10 mg/kg in the morning, 10 mg/kg at midday, and 20 mg/kg in the evening for 48 weeks. Subjects (or parent/legal guardian) will record each dose on a diary card provided by PTC Therapeutics.

After completion of the Stage 1 (Week 48), subjects will be eligible for an additional 96 weeks of open-label ataluren treatment. Subjects who received ataluren during Stage 1 will continue to receive ataluren; subjects who had been randomized to placebo will receive ataluren during Stage 2

There will be an optional sub-study at the end of the Stage 2 Open-Label Extension. Subjects will be able to consent to receive an additional 96 weeks of ataluren treatment, returning to the clinic every 24 weeks. The assessments to be conducted are outlined in the schedule of events. Subjects who choose not to participate in the sub-study will be required to complete the Post-treatment follow-up visit at the end of the Stage 2 Open-Label Extension.

[figure not shown]
The start of the sub-study will require prior approval of a protocol amendment from applicable Institutional Review Boards and will continue for 96 week or until commercial availability of ataluren for this indication, whichever is first, or until a positive risk-benefit assessment in this indication is not demonstrated.

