2.5 Sample Size

The study was planned to enroll a minimum of 36 subjects with nonsense mutation aniridia who are ≥ 2 years of age. This number of subjects has been reduced to 24 and should provide adequate information for an initial evaluation the efficacy safety of ataluren in this population.

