7.1 Sample Size

The study is planned to enroll a minimum of 36 subjects with nonsense mutation aniridia who are ≥ 2 years of age. This number of subjects should provide adequate information to evaluate the safety of ataluren in this population. For a statistical hypothesis test for any efficacy endpoint, the study will have 60% power to detect an effect size (i.e., standardized mean difference) of 0.85, or 80% power to detect an effect size of 1.06, at the 0.05 significance level (2-sided).

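### The multiple-imputation check on LOCF leaves randomised arm out of its model, so it shrinks a true treatment difference toward zero and rejects too rarely

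*SAP*

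**What the plan says.** SAP 10.1 makes LOCF the primary way of filling in the primary endpoint through Week 48, and then says: "As a sensitivity analysis to the use of LOCF, multiple imputation (using SAS PROC MI and SAS PROC MIANALYZE) will also be used". This applies to Week 48 in the ITT population, with the MCMC method, twenty imputations and a fixed seed. The predictors are listed: "Missing data predictors will be baseline MRS, MNREAD baseline parameters of reading acuity index, critical print size, reading acuity, and subject age". Arm is not among them, and nothing says that PROC MI is run by arm.

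SAP 7.7 defines the analysis that the imputed data feed, an ANCOVA in which "baseline Maximum Reading Speed (OU) and age will be included as covariates, with treatment as a fixed effect". The same section adds: "Analysis results for data with and without imputations (using methods defined in Section 10.1) will be compared". SAP 10.1 also plans a tipping-point analysis that treats the two arms differently.

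**The concern.** The imputation model lacks the one term that the analysis model is there to test. A missing ataluren value and a missing placebo value with the same baseline and age are drawn from the same distribution, a mixture of both arms' observed outcomes. That builds in no difference between arms for every subject with a missing value.

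MI is the first of the two named checks on LOCF. If a real effect exists and some Week 48 values are missing, MI leans toward no difference for a reason unrelated to the missing-data mechanism. A weak or non-significant MI result could then make a sound LOCF result look fragile. Agreement between the two would not reassure either, because LOCF also shrinks the difference when the carried value is baseline.

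**Working it through.** **Plan's own figure.** The SAP gives none for the MI analysis. Its only power statement (SAP 7.1: 36 subjects, 60% at 0.85 SD, 80% at 1.06 SD) serves here only as the source of an effect size. A two-sided t test at 24:12 gives 64.7% and 83.0%; that mismatch does not bear on this point.

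**Inputs**
- Predictors: the five in SAP 10.1. Analysis model: SAP 7.7.
- Allocation (SAP 2.4): "Eligible subjects will be randomized in a masked 2:1 fashion to either ataluren or placebo".
- Sample size (SAP 2.5): "This number of subjects has been reduced to 24", so 16:8. SAP 7.1 still has 36, so 24:12.
- Effect: 1.06 SD, an assumption. SAP 7.1 names it as detectable with 36 subjects, not as expected.
- Missing shares mA (ataluren) and mP (placebo): not in the documents, so assumed. With 8 placebo subjects, one loss is 1/8 = 12.5%.

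**Step 1: closed form.** Let the placebo mean change be 0, the ataluren mean be δ, and p the ataluren share of observed subjects. The pooled imputation mean is pδ. After imputation the arm means are (1 − mA)δ + mA·pδ and mP·pδ. Their difference is

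δ[1 − mA + (mA − mP)p], which at p = 2/3 is δ[1 − mA/3 − 2mP/3].

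With mA = mP = m it is δ(1 − m).

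**Step 2: simulation at 16:8.** 5,000 trials per scenario; 20 imputations by Bayesian normal regression; ANCOVA on arm, baseline MRS and age; Rubin's rules with Barnard-Rubin degrees of freedom (df). Assumed: values missing completely at random in fixed numbers per arm, baseline MNREAD values correlated 0.7 given age, outcome independent of covariates, LOCF carrying baseline (zero change). The formula column uses the actual p, for example 16/22 in the third row: 1 − 0.25 × 0.727 = 0.818.

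| Missing, ataluren–placebo | Formula | Kept: arm-free MI | Kept: MI with arm | Kept: LOCF | Rejection: arm-free MI / MI with arm / observed data only |
|---|---|---|---|---|---|
| 12.5%–12.5% | 0.875 | 0.86 | 1.00 | 0.87 | 30 / 46 / 53% |
| 25%–25% | 0.750 | 0.73 | 1.00 | 0.75 | 8 / 33 / 46% |
| 0%–25% | 0.818 | 0.81 | 1.00 | 1.00 | 24 / 44 / 51% |
| 25%–0% | 0.900 | 0.88 | 1.00 | 0.75 | 31 / 46 / 54% |
| 12.5%–25% | 0.788 | 0.78 | 1.01 | 0.88 | 16 / 39 / 48% |

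With one loss per arm (1 of 16, 1 of 8), arm-free MI keeps 0.88 and rejects 36%, against 49% with arm. At 24:12 and 25% each it keeps 0.73 and rejects 27%, against 59% with arm.

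**Step 3: no true effect.** Arm-free MI rejects 1.8% (12.5% each) and 0.4% (25% each). The cause is a standard error that is too large for the estimate's real spread. A second simulation at 16:8 (2,000 to 2,500 runs, baseline MRS explaining 30% of variance) gave a mean Rubin standard error of 0.512 against a true SD of 0.438 at 12.5% each, and 0.577 against 0.415 at 25% each.

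**Step 4: does the df method matter?** From that second simulation, rejection with Barnard-Rubin / ordinary Rubin df:

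| Missing per arm | Effect 1.06, arm-free | Effect 1.06, with arm | No effect, arm-free | No effect, with arm |
|---|---|---|---|---|
| 12.5% | 31.2 / 37.8% | 46.5 / 53.0% | 2.0 / 3.3% | 4.0 / 5.4% |
| 25% | 7.5 / 12.4% | 34.2 / 41.8% | 0.4 / 0.6% | 2.8 / 4.8% |

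The levels move. The gap between arm-free and with-arm MI does not shrink materially: 15.3 against 15.2 points at 12.5%, and 26.7 against 29.4 points at 25%.

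**Step 5: is LOCF cut by the same amount?** Only if the shares are equal and baseline is what is carried. If both arms also improve by 0.5 SD, at 12.5%–25% LOCF gives 0.875 × 1.56 − 0.75 × 0.5 = 0.99, and 0.99/1.06 = 0.93 (simulated 0.94), against 0.78 for arm-free MI. Nor is baseline always what is carried. Protocol 8.2 asks early discontinuers to complete the Visit 8 assessments, which include MNREAD. SAP 5 assigns that visit to the window it falls in; failing that, "then the termination visit will be assigned to the visit closest to that date". The midpoint of Days 169 and 337 is Day 253, so a later termination MNREAD counts as Week 48 and is not missing, while an earlier one can give LOCF a post-baseline value.

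**The case against.** The omission itself is hard to dispute; the case against is about size and weight.

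First, the rejection rates depend on the df method, and SAP 10.1 names only the SAS procedures with no small-sample adjustment. This stands for the levels: with ordinary df the test is less conservative, and MI with arm loses less against observed data only (41.8% against 46.0% at 25% each in the second simulation). It does not remove the bias or the gap in Step 4.

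Second, the simulations give every subject a baseline MNREAD. Entry is from age 2, Protocol 8.3.15 does not require MNREAD below age 8, and the ITT population takes in every randomised, dosed subject. Young children could enlarge the missing share or drop out of the ANCOVA. This stands, and the rejection rates should not be read as forecasts for this trial.

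Third, the consequence is narrow. The error runs against ataluren, MI is one sensitivity analysis, and it would be read beside the observed-data comparison and the tipping-point analysis. With equal losses and baseline carried, LOCF and arm-free MI give nearly the same estimate (0.87 and 0.86; 0.75 and 0.73). All true, but the tests still part: at 25% each, a run with ordinary df rejected 41% with LOCF and 13% with arm-free MI. A sound LOCF result could still look fragile.

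**Conclusion.** The point holds and is minor. Followed as written, SAP 10.1 biases the MI estimate toward zero whenever Week 48 values are missing and a real effect exists, and makes its test over-conservative. The direction does not depend on the exact missing share. The size does: about the missing share itself under equal loss, and about mA/3 + 2mP/3 otherwise. It rests on a single pooled imputation, data missing at random and assumed shares. It does not touch the primary LOCF result or the testing sequence, and it does not raise the false-positive risk.

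**What to change.** Add randomised arm to the predictors of the PROC MI model in SAP 10.1, before unmasking. This removes the bias, though not all of the power lost to missing data. The cost is one variable in the call, one phrase in the text, and a model with seven coefficients instead of six: a small loss of precision in a small sample. Dropping to arm, baseline MRS and age as predictors raised rejection from 33% to 41% at 25% missing per arm (16:8, Barnard-Rubin df), if a leaner model is wanted.

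Imputing separately by arm is not workable at this size. Five predictors and an intercept make six coefficients; 8 placebo subjects leave 7 observed outcomes after one loss (7 − 6 = 1 residual degree of freedom) and 6 after two (none).
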